6.1.2.3 Disease Control Rate (DCR)

The DCR is defined as the proportion of subjects with a CR or PR (without confirmation) or SD based on RECIST v1.1 as assessed by the blinded IRR. DCR as assessed by the local investigator will be performed as a sensitivity analysis.

Analysis of DCR with confirmation defined as the proportion of subjects with best overall response as confirmed CR, confirmed PR or SD based on the RECIST v1.1 as assessed by the blinded IRR may also be performed.

6.1.2.4 Duration of Response (DOR)

DOR is defined as the time from the date of the first response CR/PR (whichever is first recorded) as assessed by IRR to the date of radiographical progression or date of censoring. If a subject has not progressed, the subject will be censored at the date of last radiological assessment or at the date of first CR/PR if no post-baseline radiological assessment is

available. DOR will be derived for subjects with best overall response as CR or PR (without confirmation).

DOR (in days) is calculated as:

(Date of documented progression or censoring) – (Date of the first response CR/PR) +1.

To apply the cut-off date to DOR is to exclude tumor assessments after cut-off date in the analysis.

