6 ANALYSIS VARIABLES

6.1 Efficacy Endpoints

6.1.1 Primary Efficacy Endpoint

The primary endpoint is PFS assessed by the blinded IRR. For each subject, PFS is defined as the time from the date of randomization until the date of radiological disease progression (i.e., PFS#1) assessed by IRR, or until death due to any cause. If a subject has neither progressed nor died, the subject will be censored at the date of last radiological assessment or at the date of randomization if no post-baseline radiological assessment is available. Subjects who receive any further anticancer therapy for the disease before radiological progression will be censored at the date of the last radiological assessment before the anticancer therapy started. If progression or death occurs after missing 2 scheduled radiological assessments, the subject will be censored at the date of last radiological assessment or at the date of randomization if no post-baseline radiological assessment is available. Missing 2 scheduled imaging assessments is defined as the gap between two imaging assessments is more than 140 days (2.5 times the scheduled imaging assessment interval (2.5 x 56 days)).

PFS (in days) is calculated as:

(Date of death or documented Progression or censoring) – (Date of randomization) +1.

To apply the cut-off date to PFS is to exclude tumor assessments, death and anti-cancer therapy date after cut-off date in the analysis.

Note: Patient cannot be censored at "Not Evaluable (NE)". If NE is the only previous assessment, then PFS will be censored at Day 1.

Sponsor: Astellas Pharma Global Development, Inc.

ISN/Protocol 8273-CL-0302

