7.4.1 Analysis of Primary Endpoint

The primary analysis will be performed on progression-free survival as assed by the IRR (PFS#1) on the FAS. In order to compare the PFS#1 between ASP8273 and the comparator Erlotinib/Gefitinib, the null hypothesis will be constructed:

• H₀₁: PFS of ASP8273 is not better than the comparator erlotinib/gefitinib

The accompanying alternative hypothesis is:

• H₁₁: PFS of ASP8273 is better than the comparator erlotinib/gefitinib

The primary analysis will be performed when approximately 362 PFS#1 events have been observed. Comparison of ASP8273 and erlotinib/gefitinib will be tested at 1-sided significance level of 0.025.

The distribution of PFS will be estimated for each treatment arm using Kaplan-Meier methodology and compared between Arm A and Arm B using log-rank test stratified by ECOG PS (0 and 1 combined versus 2), EGFR mutation type (exon 19 vs exon 21), and TKI chosen (erlotinib versus gefitinib). In addition, stratified Cox proportional hazard model will be used to estimate the hazard ratio and the corresponding 95% confidence interval.

The sensitivity analyses for PFS include:

- The primary analysis repeated for PPS
- The primary analysis including clinical progression as an event may be performed on the FAS
- If there is a difference in the stratification values between IRT and the CRF, primary analysis may be repeated on the FAS using CRF stratification values

Sponsor: Astellas Pharma Global Development, Inc.

ISN/Protocol 8273-CL-0302

• PFS#1 as assessed by the IRR will be analyzed using restricted mean survival time (RMST) approach from time 0 to 36 months. The restricted mean is a measure of average survival from time 0 to a specified timepoint. This approach does not require any model assumptions such as proportional hazards.

Table 4 PFS#1 Definition

Situation	Date of Event or Censor	Outcome			
No evaluable post-baseline imaging assessments, no death	Date of randomization	Censor			
Subject did not receive new anti-cancer therapy:					
Radiographical progression documented per RECIST v1.1	Date of radiological PD	Event			
No radiographical progression, but death recorded on eCRF	Date of death	Event			
No radiographical progression nor death	Date of last radiological assessment or at the date of randomization if no post-baseline radiological assessment is available	Censor			
Subject received new anti-cancer (ACT)	therapy:				

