Radiographical progression documented per RECIST v1.1 after new ACT	Date of last radiological assessment before start of new anti-cancer therapy or at the date of randomization if no post-baseline radiological assessment is available	Censor			
Radiographical progression documented per RECIST v1.1 before new ACT	Date of radiological PD	Event			
No radiographical progression before new ACT but death recorded	Date of last radiological assessment before start of new anti-cancer therapy or at the date of randomization if no post-baseline radiological assessment is available	Censor			
No radiographical progression nor death	Date of last radiological assessment before start of new anti-cancer therapy or at the date of randomization if no post-baseline radiological assessment is available	Censor			
Missed 2 scheduled radiological assessm	ents:				
If radiographical progression or death occurs after missing 2 scheduled radiological assessments	Date of last radiological assessment or at the date of randomization if no post-baseline radiological assessment is available	Censor			

PFS#1 = Date of Event or Censor – Date of Randomization +1

In addition, since it is likely that K-M curves of PFS#1 as assessed by IRR will separate late in the study, Harrington-Fleming test will be performed as exploratory analysis with prespecified weight of p=0 and q=0.5. Different weights may be used as well.

Sponsor: Astellas Pharma Global Development, Inc.

ISN/Protocol 8273-CL-0302

To investigate non-proportionality between the treatment arms, the LOG(–LOG) survivor function versus time curves will be plotted. The scaled Schoenfeld residuals by time plot will be examined for evidence of a non-zero correlation, which indicates non-proportionality. Piecewise Cox models may be explored given evidence of non-proportional hazards.

Hochberg procedure will be used to control the overall error rate at 1-sided 0.025 level for the secondary efficacy endpoints (OS and ORR). Only when the primary endpoint significantly favors the ASP8273 arm will secondary endpoints be tested.

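### Duration of response ends only at radiographic progression, so a responder who dies without it is censored at the last scan, although PFS by the same central reader generally counts that death.

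*SAP*

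**What the plan says.** Protocol 7.4.2.5 and SAP 6.1.2.4 both run DOR from the first CR or PR by independent radiologic review (IRR) to radiographic progression or censoring. On censoring, SAP 6.1.2.4 states: "If a subject has not progressed, the subject will be censored at the date of last radiological assessment". If there is no later scan, the date of first CR or PR is used. The DOR formula contains a progression or censoring date but no death date. The cut-off rule is limited in the same way: "To apply the cut-off date to DOR is to exclude tumor assessments after cut-off date in the analysis". SAP Table 6 has two rows: progression is an event, and no progression is censored.

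The primary endpoint is built differently. In SAP 6.1.1, PFS runs to progression "assessed by IRR, or until death due to any cause", and its cut-off rule reads: "To apply the cut-off date to PFS is to exclude tumor assessments, death and anti-cancer therapy date after cut-off date in the analysis". SAP Table 4 has a row for "No radiographical progression, but death recorded on eCRF", with the date of death as an event. Two groups of deaths are censored in PFS: those described by "No radiographical progression before new ACT but death recorded", and those after two missed scheduled assessments.

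DOR is a secondary endpoint. It is compared between arms by stratified log-rank test and Cox model (Protocol synopsis, Efficacy; SAP 7.4.1.5) and summarised by subgroup (SAP 7.8).

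**The concern.** OS, PFS by IRR, PFS by the investigator and PFS#2 all count death. DOR is the only time-to-event efficacy endpoint that does not. Neither document gives a reason or plans a DOR analysis that counts death.

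Such deaths are foreseeable. Table 4 provides for death without progression. Protocol 6.1 lets treatment stop for clinical progression, or for investigator-assessed progression that the central reader has not confirmed. Post-treatment imaging then ends once the investigator records progression. A responder who follows that path and dies before new therapy or two missed scans is a PFS event but a censored DOR.

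At stake is what the DOR figures mean. A response cut short by death is handled like one still being followed. A reader who takes DOR as time in response until progression or death would find it too favourable. Because DOR is also compared between arms, a difference in the frequency of such deaths would enter the hazard ratio.

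**Working it through.** The documents give no expected DOR, responder count or DOR event count, so there is no planned figure to reproduce.

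**Step 1. The rules side by side.**

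| Item | DOR (SAP 6.1.2.4, Table 6) | PFS by IRR (SAP 6.1.1, Table 4) |
|---|---|---|
| Progression | Event | Event |
| Death, no progression, no new therapy | Censored at last scan | Event at death |
| Death after new therapy, no prior progression | Censored at last scan | Censored at last scan before the therapy |
| Progression or death after two missed scans | No rule | Censored at last scan |
| Data removed after cut-off | Tumor assessments | Tumor assessments, death, therapy date |

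Under the present DOR rule the missing Table 4 rows matter little. The missed-scan row could change only a progression found after a long gap, and imaging after study drug stops ends at new therapy (Protocol 5.3). Both rows are needed once death counts.

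**Step 2. One patient.** First PR at the day-56 scan, death on day 100, no progression, no new therapy, next scan not yet due.
- PFS: event at day 100.
- DOR as planned: 56 - 56 + 1 = 1 day, censored.
- DOR with death as an event: 100 - 56 + 1 = 45 days, event.

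**Step 3. Effect on the median.** Let f be the share of response-ending events that are deaths PFS would count but DOR censors. Assume constant, independent hazards with total rate λ, so the progression-or-death median is M = ln 2/λ. Censoring the deaths leaves rate (1-f)λ and a median of M/(1-f). f is assumed, and the design PFS medians (10.4 and 15.6 months) stand in for M.

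| Assumed f | 1/(1-f) | M = 10.4 | M = 15.6 |
|---|---|---|---|
| 2% | 1.02 | 10.61 | 15.92 |
| 5% | 1.05 | 10.95 | 16.42 |
| 10% | 1.11 | 11.56 | 17.33 |

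A simulation with progression detected on a 56-day scan grid, M = 10.4 and assumed administrative censoring at 12 to 36 months raised the 12-month DOR by about 1, 2 and 4 percentage points respectively.

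**Step 4. Effect on the hazard ratio.** The progression-or-death hazard ratio is multiplied by (1-fA)/(1-fB).
- Equal f, for example 0.95/0.95 = 1.00: no change.
- 5% in one arm against 2% in the other: 0.95/0.98 = 0.97.
- 10% against 5%: 0.90/0.95 = 0.95.

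The factor favours the arm with more such deaths.

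**Step 5. Is the direction certain in a sample?** Take three responders: progression at day 90, progression at day 200, and a third last scanned before day 90 who dies on day 100.
- As planned: the third has left the risk set by day 90, so the curve falls to 1/2 there. The median is 90 days.
- With death as an event: the curve is 2/3 after day 90 and 1/3 after day 100. The median is 100 days.

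The planned estimate can therefore be the shorter one, because censoring is back-dated to the last scan. This is a small-sample effect. In 600 simulated trials at each f in Step 3 (assumed 200 responders, M = 10.4, 7-day scan windows), the planned median was never shorter.

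**The case against.** The strongest reply is that this is a choice of estimand. Time to progression among responders is well defined, the protocol and SAP agree on it, and programming is unambiguous. No passage requires death to end a response, and deaths are already captured in PFS and OS. That stands as far as it goes: a reader might infer a protocol-SAP conflict, and there is none. It does not explain why DOR alone omits death, and the plan has no version of DOR that counts it.

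The size is also assumed. At f = 20% the same formula gives 1/0.80 = 1.25, or +25%, so the result depends on the choice of f. In the 200-responder simulations the typical change in the Kaplan-Meier median was about 2 days at f = 2% and 5 days at f = 5%, but about 48 days at f = 10%, because the median tends to jump between scan dates. No single figure should be quoted as the expected overstatement.

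Two stronger readings are tempting. One is that reported DOR can never be shorter than the progression-or-death duration; Step 5 shows that this fails for a Kaplan-Meier estimate. The other is that the arm comparison is biased; that needs f to differ between arms, and nothing in the documents says that it does.

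Consequences are limited. DOR is outside the Hochberg family and is compared only among responders, a group defined after randomization.

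**Conclusion.** The point holds, and the definition should be changed. As written, DOR is time to IRR progression with deaths censored, and it differs without explanation from PFS by the same reader. If deaths without progression occur among responders, reported DOR will generally be no shorter than the progression-or-death duration.

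The illustrative +2%, +5% and +11% on the median rest on constant independent hazards and an assumed f. They measure the gap between two estimands; they do not estimate dependent censoring. The hazard ratio is unchanged when f is equal in both arms, and otherwise shifts towards the arm with more such deaths. The primary PFS, OS and ORR tests are not affected by the DOR rule.

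**What to change.** Define DOR as first IRR CR or PR to IRR progression or death from any cause, whichever is first. In the SAP:
- Add a row to Table 6: death without progression is an event at the date of death.
- Add death to the DOR formula, and death and anticancer therapy date to the DOR cut-off rule.
- Apply Table 4's censoring for new therapy and for two missed scans.
- Settle the missed-scan gap for deaths. SAP 6.1.1 says: "Missing 2 scheduled imaging assessments is defined as the gap between two imaging assessments is more than 140 days". A death is not an imaging assessment. State once, in 6.1.1 and for both PFS and DOR, that for a death the gap runs from the last evaluable assessment to the date of death. With scans on schedule, two assessments are at most 56 + 7 + 7 = 70 days apart. This clarifies the primary PFS derivation, so it must be fixed before treatment codes are released.
- Extend the death-date imputation rule in 7.10.1, which names only OS, to PFS and DOR together. Adding DOR alone would create a new mismatch with PFS.
- Keep the progression-only rule as a labelled sensitivity analysis.

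Align Protocol 7.4.2.5 at the next amendment. Until then, enter the death-as-event analysis in the SAP as a pre-specified sensitivity analysis, so that the two documents do not conflict.

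No new data are needed, because death dates are already collected. SAP section 1 allows revision before database hard lock. The protocol edit affects the evaluation of efficacy and needs IRB/IEC approval under Protocol 8.3.3, but can be bundled with other changes. The cost is a small amount of programming and a slightly less favourable reported DOR.

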6.1.2.5 PFS#1 as assessed by Local Investigator

See Section 6.1.1 for the definition of PFS#1. Tumor assessments as assessed by local investigator will be used in the derivation of PFS.

6.1.3 Exploratory Efficacy Endpoint

6.1.3.1 PFS on Next-line therapy (PFS#2)

PFS#2 is defined as the time from initiation of new systemic anti-cancer treatment (excluding local radiation, surgical removal of metastatic site or protocol defined Erlotinib or Gefitinib or ASP8273 based on initial treatment allocation per subject) to investigator-determined progression, discontinuation of new treatment, start of a different treatment or death from any cause, whichever comes first. Otherwise, subjects will be censored.

Subjects who have not started new systemic anti-cancer treatment will be censored at Day 1. Subjects who are alive, started new systemic anti-cancer treatment and for whom a PFS#2 event has not been observed should be censored at the last time known to be alive.

PFS#2 (in days) is calculated as:

(Date of death or investigator-determined progression on next-line therapy or discontinuation of next-line therapy or started another therapy or censoring) – (Date of randomization) +1.

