7.4.3 Analysis of Exploratory Endpoints

7.4.3.1 PFS on Next-Line Therapy (PFS#2)

PFS#2 is defined as the time from initiation of new systemic anti-cancer treatment (excluding local radiation, surgical removal of metastatic site or protocol defined Erlotinib or Gefitinib or ASP8273 based on initial treatment allocation per subject) to investigator-determined progression, discontinuation of new treatment, start of a different treatment or death from any cause, whichever comes first. Otherwise, subjects will be censored.

Subjects who have not started new systemic anti-cancer treatment will be censored at Day 1. Subjects who are alive, started new systemic anti-cancer treatment and for whom a PFS#2 event has not been observed should be censored at the last time known to be alive.

The distribution of PFS#2 will be estimated for each treatment arm using Kaplan-Meier methodology and compared between Arm A and Arm B using stratified log-rank test as specified in [Section [7.4.1.1](#)]. In addition, stratified Cox proportional hazard model will be used to estimate the hazard ratio and the corresponding 95% confidence interval.

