1 INTRODUCTION

This Statistical Analysis Plan (SAP) contains a more technical and detailed elaboration of the principal features of the analysis described in the protocol, and includes detailed procedures for executing the statistical analysis of the primary and secondary endpoints and other data.

The SAP is finalized and signed prior to any of the following: study unblinding, database hard lock, interim analysis, or accumulation of substantial amount of data in an open-label study to ensure lack of bias. For operational efficiency an earlier time is usually targeted and wherever possible, the SAP should be developed in parallel with protocol finalization. For Phase 2-4 studies the SAP should be developed and approved before First Subject In (FSI). If the expected interval between FSI and soft-lock is less than 12 weeks, then the SAP should be approved by 12 weeks prior to the planned date of soft-lock. If needed, revisions to the approved SAP may be made prior to database hard lock. Revisions will be version controlled.

This statistical analysis is coordinated by the responsible biostatistician of APGD-US. Any changes from the analyses planned in the SAP will be justified in the Clinical Study Report (CSR).

Prior to database hard lock, a final review of data and TLFs meeting will be held to allow a review of the clinical trial data and to verify the data that will be used for analysis set classification. If required, consequences for the statistical analysis will be discussed and documented. A meeting to determine analysis set classifications may also be held prior to database hard lock.

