3.2 Study Design

3.2.1 Study Design

This multinational, open-label randomized study will evaluate ASP8273 compared to erlotinib or gefitinib (1st generation EGFR TKI) as first line therapy in subjects with locally advanced, metastatic or unresectable stage IIIB/IV adenocarcinoma NSCLC (newly diagnosed or recurrent) with EGFR activating mutations (exon 19 deletion or exon 21 L858R), with or without a T790M mutation, who have not previously been treated with an EGFR inhibitor (1st line).

PFS by IRR is the primary variable. Secondary variables include OS, ORR, PFS by the investigator, DCR, safety and QoL/PRO. Exploratory variables include biomarkers, pharmacokinetics and PFS#2 on subsequent therapy.

Approximately 600 subjects will be randomized 1:1 to 1 of 2 treatment arms (Arm A or Arm B). Arm A will receive 300 mg daily of ASP8273 and Arm B will receive either 150 mg erlotinib or 250 mg gefitinib daily, as decided by the investigator prior to randomization. Both arms will follow 28-day cycles of continuous dosing. Subjects will be stratified according to the following: ECOG PS (0, 1 or 2), EGFR mutation status (exon 19

deletion or mutations in exon 21 [L858R]), TKI chosen (erlotinib or gefitinib) and race (Asian versus non-Asian).

Screening will take place up to 28 days prior to subject randomization on cycle 1 day 1. Subjects will start with cycle 1 and continue on to subsequent 28-day cycles until 1 of the discontinuation criteria are met. Subjects will visit the clinic for evaluations on day 1 and day 15 of treatment cycle 1 and then on day 1 of subsequent treatment cycles up to cycle 7. Subjects who continue past cycle 7 will have visits on day 1 of each odd-numbered cycle.

Quality of life will be assessed during each treatment cycle where a visit takes place, at the follow-up visit, and at each of the post-treatment or long-term follow-up survival contacts for 6 months after treatment discontinuation (EQ-5D-5L only).

Imaging will be evaluated at baseline and every 56 days (± 7 days) throughout the study. A blinded independent central reader will review all imaging scans to confirm complete response (CR), partial response (PR), stable disease (SD) or progressive disease (PD) per Response Evaluation Criteria in Solid Tumors (RECIST) V1.1. Disease progression on study drug (PFS#1) should be confirmed by the blinded independent central reader before subjects are discontinued from treatment.

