7 STATISTICAL METHODOLOGY

7.1 General Considerations

For continuous variables, descriptive statistics will include the number of subjects (n), mean, standard deviation, median, minimum and maximum. When needed, the use of other percentiles (e.g., 10%, 25%, 75% and 90%) will be mentioned in the relevant section. Frequencies and percentages will be displayed for categorical data. Percentages by categories will be based on the number of subjects with no missing data, i.e. will add up to 100%. Kaplan-Meier survival curves will be displayed for time-to-event variables and median survival time will be estimated with 2-sided 95% confidence interval (CI).

Summaries based on FAS and PPS (e.g. disposition, baseline and efficacy data) will be presented by planned treatment, unless specifically stated otherwise. Safety analysis and other summaries based on SAF, PKAS or PDAS will be presented by actual treatment received.

All statistical comparisons will be made using one sided test at the α =0.025 significance level unless specifically stated otherwise. All null hypotheses will be Arm A is not better than Arm B, all alternative hypotheses will be Arm A is better than Arm B, unless specifically stated otherwise.

All data processing, summarization, and analyses will be performed using SAS® Version 9.2 or higher on Unix. Specifications for table, figure, and data listing formats can be found in the TLF specifications for this study.

Study day for safety assessments (e.g. laboratory assessment, onset of adverse events, vital signs, etc.) will be calculated in reference to the first dose date. For assessments conducted before the first dose, study day will be calculated as (assessment date – first dose date). For assessments conducted on or after the first dose, study day will be calculated as (assessment date – first dose date \pm 1).

Study day for efficacy assessments (imaging assessment, overall survival, tumor response, etc.) will be calculated in reference to the randomization date. For assessments conducted before randomization, study day will be calculated as (assessment date – randomization date). For assessments conducted on or after randomization, study day will be calculated as (assessment date – randomization date + 1).

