7.4.2 Analysis of Exploratory Endpoint

7.4.2.1 PFS#2

The distribution of PFS#2 will be estimated on the FAS for each treatment arm using Kaplan-Meier methodology and compared between Arm A and Arm B using stratified log-rank test as specified in [Section 7.4.1]. In addition, stratified Cox proportional hazard model will be used to estimate the hazard ratio and the corresponding 95% confidence interval.

Table 7 PFS#2 Definition

Situation	Date of Event or Censor	Outcome
Subject did not receive new anti-cancer	Day 1	Censor
therapy		
Subject received new anti-cancer therapy:		
Subject has investigator-determined	Minimum of [Date of	Event
progression on that treatment or ended that	investigator determined PD, date	
treatment or started another therapy or death	of death, new ACT end date, or	
	start date of another therapy]	
Subject did not die nor progressed nor	Last known alive date	Censor
stopped the new ACT nor started another		
therapy at the time of analysis cutoff date		

PFS#2 = Date of Event or Censor – Date of initiation of new systemic anti-cancer treatment +1

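### SAP 6.1.3.1 defines PFS#2 from the start of next-line therapy, but its calculation line subtracts the randomization date

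*SAP*

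**What the plan says.** Four current statements fix the time origin of PFS#2.

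- Protocol 7.4.3.1: "PFS#2 is defined as the time from initiation of new systemic anti-cancer treatment", ending at investigator-determined progression, end of the new treatment, start of a different treatment, or death.
- SAP 6.1.3.1, definition: the same origin and the same events.
- SAP 6.1.3.1, calculation line at the end of the section: event or censoring date on "next-line therapy or started another therapy or censoring) – (Date of randomization) +1".
- SAP 7.4.2.1, footer of Table 7: event or censoring date minus "Date of initiation of new systemic anti-cancer treatment +1".

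For subjects who never start next-line therapy, SAP 6.1.3.1 says: "Subjects who have not started new systemic anti-cancer treatment will be censored at Day 1". Table 7 has a row with the same rule. SAP 7.1 adds: "Study day for efficacy assessments (imaging assessment, overall survival, tumor response, etc.) will be calculated in reference to the randomization date".

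On the standing of the endpoint, SAP 3.2.1 says: "Exploratory variables include biomarkers, pharmacokinetics and PFS#2 on subsequent therapy". SAP 7.4.1 applies the Hochberg procedure "at 1-sided 0.025 level for the secondary efficacy endpoints (OS and ORR"), so PFS#2 is outside the tested family. SAP 7.4.2.1 nevertheless compares the arms on the FAS by stratified log-rank test and stratified Cox model.

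**The concern.** One endpoint has two written calculation rules, and they give the same value only when next-line therapy starts on the day of randomization. SAP 6.1.3.1 is where the endpoint variable is derived, so its calculation line is a natural source for a programmer.

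Counting from randomization adds the first-line period to each subject's PFS#2. No subject can have a PFS#2 event during that period, and its length depends on how well first-line treatment worked. If ASP8273 prolongs PFS#1, its arm would look better on PFS#2 even if next-line outcome were identical. The exploratory objective is the impact of subsequent therapy, and this reading would confuse that with the first-line effect already measured by the primary endpoint.

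A smaller, related point concerns subjects with no next-line therapy. They have no initiation date, so the Table 7 formula cannot be applied to them literally, and the SAP does not state the value they receive.

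**Working it through.** The documents give no power, event count or expected result for PFS#2, so there is no stated figure to reproduce. The check sets the rules side by side and then sizes the difference.

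**1. The two rules.** Let R be the randomization date, S the start of new systemic treatment and E the event or censoring date.

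| Source | PFS#2 in days |
|---|---|
| Protocol 7.4.3.1, SAP 6.1.3.1 definition | time from S to E |
| SAP Table 7 footer | E − S + 1 |
| SAP 6.1.3.1 calculation line | E − R + 1 |

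The difference is (E − R + 1) − (E − S + 1) = S − R, the time from randomization to the start of next-line therapy.

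**2. Example with assumed dates.** R = 1 July 2016, S = 1 July 2017, E = 1 December 2017. Table 7 gives 154 days. The 6.1.3.1 line gives 519 days. The difference, 519 − 154 = 365 days, is exactly S − R.

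**3. Simulation at the planned analysis time.**

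From the documents: 600 subjects randomized 1:1; PFS#1 medians of 15.6 months (Arm A) and 10.4 months (Arm B); primary analysis about 36 months after the first randomization.

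Assumed: exponential times; uniform accrual over 22, 24 or 26 months, which gives 412 to 436 PFS#1 events by month 36, close to the planned 420; next-line PFS with a median of 4, 6 or 9 months and a true hazard ratio of 1; three levels of next-line uptake and lag. The Cox and log-rank analyses were unstratified, whereas the SAP stratifies. Each uptake level has 9 scenarios of 2000 runs.

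| Uptake after PFS#1, lag | HR, 6.1.3.1 line | p<0.025, 6.1.3.1 line | p<0.025, Table 7 |
|---|---|---|---|
| 50%, 1 month | 0.873–0.897 | 8.3–13.8% | 1.9–2.9% |
| 70%, 1 month | 0.872–0.895 | 9.9–18.6% | 1.8–2.8% |
| 100%, none | 0.867–0.898 | 12.5–26.7% | 1.6–3.2% |

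The p-values are nominal, one-sided, in favour of ASP8273. At 70% uptake the Table 7 formula gave an HR of 0.992 to 1.005. The simulation error of a percentage such as 18.6% is √(0.186 × 0.814 / 2000), or about 0.9 points.

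At 70% uptake the 6.1.3.1 line adds a median of 9.1 to 9.8 months in Arm A and 7.9 to 8.4 months in Arm B.

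**4. Control.** With no first-line effect (both PFS#1 medians 13 months, 70% uptake, 24-month accrual, next-line median 6 months), the HR is 1.00 under both formulas, with p<0.025 in 3.0% (6.1.3.1 line) and 2.4% (Table 7). The bias therefore comes from the first-line difference.

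**5. Dependence on follow-up.** At 36 months the subjects who have started next-line therapy are those who progressed early in either arm, which mutes the contrast. With 24-month accrual, next-line median 6 months and 70% uptake, the HR under the 6.1.3.1 line falls to 0.81 at a 60-month cutoff and 0.71 at 120 months. With no censoring and everyone starting next-line therapy at PFS#1, it is 0.67, 0.69 and 0.72 for next-line medians of 3, 6 and 9 months.

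**6. Subjects with no next-line therapy.** By month 36 they number 302 to 318 of 600 (50 to 53%) at 70% uptake, and 165 to 188 (27 to 31%) at full uptake. With continuous times, censoring them at day 1 leaves the log HR unchanged, because they leave the risk set before any event. With times in whole days, an event on the day of initiation can tie with them, but the log HR then moves by at most 0.009.

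**The case against.** Three of the four statements agree on the origin. Table 7 sits in the analysis section, has a complete set of event and censoring rules and carries the right formula, so a programmer who works from 7.4.2.1 gets the right answer. The false-positive percentages apply only if the odd line out is used, and they concern a nominal p-value on an exploratory endpoint for which no error control is claimed. Uptake, lag, accrual and next-line medians are all assumed. This stands, and it limits the severity. It does not remove the contradiction: the line is complete, current and wrong as written.

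The point about subjects with no next-line therapy is weaker. Both SAP 6.1.3.1 and Table 7 say they are censored at Day 1, the SAP uses the same phrase for PFS#1 when the only assessment is not evaluable, and with the plus-one convention it most naturally means a value of 1 day. The SAP 7.1 sentence concerns the numbering of assessment days and need not fix the origin of every time-to-event endpoint; duration of response, for example, runs from first response. Stating the value is therefore optional tidying and has no material effect on the result.

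**Conclusion.** The contradiction is real and can be confirmed from the text alone. The calculation line in SAP 6.1.3.1 is the only current rule that counts PFS#2 from randomization. The amendment log shows that a superseded protocol definition did so, which suggests a leftover, but that is an inference and the conclusion does not depend on it.

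If the line were used, equal next-line outcome would appear as a hazard ratio of about 0.87 to 0.90 at a 36-month cutoff, with nominal significance in 8 to 27% of runs across the assumed uptake levels instead of about 2 to 3%. The bias would grow with longer follow-up. These sizes rest on the planned PFS#1 effect being present and on the assumptions listed above; the direction follows from the formula.

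The correction should be made, but it is not critical. PFS#2 is exploratory, so the primary analysis, its power and the control of type I error for PFS, OS and ORR are unaffected.

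**What to change.** In the calculation line of SAP 6.1.3.1, replace the randomization date with the Table 7 term, so that the line subtracts "Date of initiation of new systemic anti-cancer treatment +1". This brings it into agreement with the definition above it, with Table 7 and with Protocol 7.4.3.1.

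Optionally, add one sentence to SAP 6.1.3.1 and Table 7: *A subject with no new systemic treatment has no start date for PFS#2 and is assigned a value of 1 day, censored.*

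The cost is one replaced term and, if wanted, one sentence. SAP section 1 provides the route: "revisions to the approved SAP may be made prior to database hard lock. Revisions will be version controlled". No protocol amendment and no new data are needed. Making the change before treatment codes are released avoids having to choose between two written formulas once results can be seen.
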